## Methods

The study will be carried out at Svärdsjö Primary Health Care Centre, during May 2018 to April 2019, as a pragmatic randomized controlled trial. Participating patients will be recruited by local advertisement at the clinic, in the nearby society, in the local advertisement bulletin and local social media groups. Inclusion criteria are: patients listed at the health care centre, wish to improve blood lipoproteins, ages 18-99 years. Exclusion criteria are: drugs affecting lipid metabolism (statins, ezetimibe, fibrates, PCSK9 inhibitors, neuroleptics, cortisone, amiodarone, estrogen, progesterone, testosterone, cyclosporin, tacrolimus, loop diuretics, protease inhibitors and anti-convulsants, whereas beta-blockers, tiazid-diuretics and SGLT2 inhibitors are accepted at stable use), malignant disease, extreme diet (vegan diet, strict low-carbohydrate diet, other weight-loss diet), disturbed metabolism e.g. untreated hypothyroidism or hyperthyroidism, dementia or inability to understand written Swedish instructions, other participant from same household, employment at the health care centre.

The participants will be block randomized after providing oral and written informed consent to either active intervention or control group (blind to researchers, personnel and participants at study start). If more than one potential participant belong to the same household, only one will be included in the study (by coin toss). All participants will receive an opaque envelope,

provided by an external source that construct the randomization sequence (Uppsala Clinical Research Center). The envelopes contain one double-sided A4 paper containing written dietary advice and some motivational strategies: “It's great that you want to improve your blood lipids! What are your three main reasons that you want to improve your blood lipids? What food choices suit you? How low can you go?” and a table in which participants are instructed to mark each day they have performed specific dietary changes. The intervention group receive detailed information on which food choices that have been demonstrated to beneficially affect LDL cholesterol, in accordance with current dietary recommendations and a recently performed systematic review of the literature (unpublished data). The control group will receive corresponding information, but instead on which food choices are known to reduce fasting triglycerides – advice neutral for LDL cholesterol (and vice versa).

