### **Statistical analyses**

Based on previous randomized intervention studies of dietary fat quality and effects on lipoproteins, at least n=222 participants are required (for alpha = 0.05 and beta = 0.10) to detect an effect in LDL cholesterol of 0.175 mmol/L (~5%), which is an effect slightly exceeding that in most previous studies, parallels within-individual day-to-day variation (at double sampling), and has some clinical significance. This calculation takes into account a 20% loss to follow-up in the intervention group and a contamination effect of 5% in the control group.

The results will be analyzed according to intention-to-treat principle. Missing data at follow-up will be handled by imputing the baseline value. For LDL cholesterol, the mean value of the double analyses at days -3/0, 18/21 and 180/183 will be used. The CV of the biological variation will thus be decreased from 7 to 5%. Between-group comparisons for effects on all outcomes will be performed as a generalized linear model (GLM) in SPSS software, adjusted for factors *a priori* considered likely to modify effects (baseline values, BMI, age and sex). As sensitivity analyses, also unadjusted, non-parametric testing (Mann-Whitney U-test) will be performed. P<0.05 will be considered as statistically significant.

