For LDL Cholesterol baseline (BL) values will be calculated as the arithmetic mean of values at day -3 and day 0 [(d-3+d0)/2], similarly, values at 3 weeks will be calculated as the arithmetic mean of values at days 18 and 21 [(d18+d21)/2] and values at 6 months will be calculated as the arithmetic mean of values at days 180 and 183 [(d180+d183)/2].

For all continuous variables, absolute change from baseline (Δ) will be calculated at 3 weeks and 6 months as [Δ = 3w - BL and 6m - BL]. Relative change from baseline (% Δ) will be calculated as [% Δ = (3w - BL)/BL and (6m - BL)/BL].

As a sensitivity analysis, variables in the GLM with non-normal distribution will be log transformed (otherwise, no transformations will be performed).

Analysis methods

27a. Analysis methods and presentation of results

Between-group differences for change from baseline (Δ) in continuous variables will be significance tested using a general linear model (GLM). For LDL cholesterol, the results will be presented as a figure with boxplots displaying values at BL, 3 weeks and 6 months for each group. Also, a boxplot of Δ -values at 6 months will be presented for each group. The results will be given in a table format, displayed as mean±SD change from baseline, and P-values for difference between groups.

Difference in mean change from baseline in LDL cholesterol (and triglycerides for control group) between 21 and 18 days and 183 vs. 180 days will be analyzed with t-tests.

Secondary outcome no. 4 (success rate) i.e. the no. and proportion of individuals that achieve a $\leq 0\%$, >0 to <10% or $\geq 10\%$ reduction in LDL cholesterol from baseline will be analyzed by logistic regression, adjusted for age, sex and baseline BMI. No. of individuals that develop impaired fasting glucose will be compared between groups with Fisher's exact test (unadjusted).

Secondary outcome no. 8 (effective food choices) will be analyzed and presented as linear regressions between number of X:s for food choices 1-13 (and the total number of X:s) and change in LDL cholesterol (or Triglycerides within Control group) at 3 weeks and 6 months.

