Secondary outcome no. 9 (stated reasons) will be categorized into main groups of reasons according to given responses (one, two or three compared to none stated), no. in each group and mean changes in LDL cholesterol (or triglycerides) as well as total number of X:s (and proportions of total number of possible X:s for both groups combined) will be given as means+SD in table format. For within-group effects on mean LDL cholesterol at 3 weeks and 6 months, paired t-tests will be performed in intervention group (the same for triglycerides in control group). For proportion of total X:s, differences compared with reference group (none stated) will be analyzed by Mann Whitney U-test.

27b. Adjustment for covariates

Comparisons of means in the GLM will be adjusted for the baseline value of the variable, baseline BMI, age and sex.

For success rate, the logistic regression will be adjusted for the covariates baseline LDL cholesterol, baseline BMI, age and sex.

Linear regressions for food choices and lipoproteins will be unadjusted.

27c. Tests for assumptions

Normality of data will be determined by visual inspection of histograms and QQ-plots. No other tests for assumptions will performed. The underlying assumptions of the GLM will be tested by examining residuals.

27d. Alternative methods if distributional assumptions do not hold

As a sensitivity analysis, variables in the GLM with non-normal distribution will be log transformed (otherwise, no transformations will be performed).

27e. Planned sensitivity analyses

For all comparisons of means of continuous outcomes, unadjusted Mann Whitney U-tests will be performed as sensitivity analyses.

27f. Planned subgroup analyses

In order to investigate whether different baseline characteristics are associated with success rate (outcome no. 4), responders (≥10% decrease in LDL cholesterol or Triglycerides) and non-responders at 3 weeks will be analyzed with descriptive statistics regarding age, sex, baseline cholesterol, no. with diabetes and impaired fasting glucose, systolic and diastolic blood pressure, no. of X:s (total and for each food choice), and reasons stated (according to categories), separately for both study arms. Comparisons between responders and non-responders will be analyzed by t-tests and Fisher's exact test. Similar analyses will be performed for successful individuals at 6 months (≥10% decrease in LDL cholesterol or Triglycerides).

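### SAP 27f compares responders with non-responders inside each arm, so it cannot separate predictors of response to the advice from predictors of ordinary LDL variation; the control-arm LDL that could do so is already collected

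*SAP*

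**What the plan says.** SAP 27f states its aim as "In order to investigate whether different baseline characteristics are associated with success rate (outcome no. 4"). The method is that "responders (≥10% decrease in LDL cholesterol or Triglycerides) and non-responders at 3 weeks will be analyzed with descriptive statistics", and the contrast is made "separately for both study arms. Comparisons between responders and non-responders will be analyzed by t-tests" and Fisher's exact test. The same is planned at the later visit: "Similar analyses will be performed for successful individuals at 6 months (≥10% decrease in LDL cholesterol or Triglycerides").

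The characteristics listed are age, sex, baseline cholesterol, diabetes, impaired fasting glucose, blood pressure, the number of X:s in the food record, and stated reasons. BMI is not listed. 27f does not say which lipid defines response in which arm. The likelier reading is LDL in the advice arm and triglycerides in the control arm, because 27a makes that split for the food-choice analysis.

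LDL is available in both arms at all three times: 27a plans "boxplots displaying values at BL, 3 weeks and 6 months for each group". Protocol, Methods, describes the control sheet as "advice neutral for LDL cholesterol (and vice versa").

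Protocol, Statistical analyses, calls the GLM covariates factors "considered likely to modify effects (baseline values, BMI, age and sex"). The GLM and the logistic regression in SAP 27a and 27b adjust for covariates but contain no interaction. The only planned look at effect modification is the second part of 27f, age under 65 against 65 and over, and it names no model or interaction test.

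**The concern.** A fall of 10% or more combines any effect of the advice with ordinary within-person variation. Inside the advice arm alone the two cannot be told apart. A factor that goes with LDL change whether or not a person was advised therefore produces the same responder/non-responder difference as a factor that changes the effect of the advice.

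Baseline LDL is a special case. It is the denominator of the percentage change, so a person whose baseline happened to read high is more likely to fall by 10%. Responders will then tend to have higher baseline LDL even if the advice works equally well for everyone.

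At stake is how the tables are read. Labelled responders and success, they are likely to be taken as a guide to who gains from written advice. As planned they cannot support that.

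**Working it through.** **1. The plan's own variability figure.** The protocol gives a biological CV of 7% for one sample and 5% for the mean of two. Check: 7/√2 = 4.95%, which rounds to 5%.

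**2. How often a 10% fall occurs with no advice effect.** SD of percentage change = CV × √2 = 5% × 1.414 = 7.07%.
- No effect: Φ(−10/7.07) = Φ(−1.414) = 7.9%, about 4 of 56.
- Planned effect of 5%, the same for everyone: Φ((−10+5)/7.07) = Φ(−0.707) = 24.0%, about 13 of 56.
- Ratio: 7.9/24.0 = 33%.

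**3. The same with the SD implied by the sample size.** The documents give no SD for LDL change, so this is an assumption. Take SD = 0.30 mmol/L and n per arm = 2(z₁+z₂)²SD²/0.175².
- 80% power: 2 × 7.849 × 0.09/0.0306 = 46.1, so 47 per arm and 94 in total (stated: 94 without contamination). Dividing by 0.95² gives 104 (stated: 106).
- 90% power: 61.8, so 62 per arm and 124 in total. Dividing by (1 − 0.20 − 0.05)² gives 220 (stated: 222).

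The fit is close but not exact. The planned effect of 0.175 mmol/L at about 5% implies an LDL of about 3.5 mmol/L, so the SD is 0.30/3.5 = 8.57%.
- No effect: Φ(−1.167) = 12.2%.
- Planned effect: Φ(−0.583) = 28.0%.
- Ratio: 43%.

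The protocol's Background quotes effects of 0.07 to 0.16 mmol/L in previous studies. Over the two SDs, 0.16 gives ratios of about 36 to 46%, and 0.07 gives about 61 to 69%.

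**4. Baseline LDL under 27f.** Simulated with about 56 per arm and an advice effect of 0% or 5%, the same proportion at every baseline, so there is no modification. Assumptions not in the documents: between-person SD 0.6 to 1.0 mmol/L; CV 5 to 6.1% (6.1% = 8.57%/√2).
- The within-arm t-test on baseline LDL is significant in about 9 to 26% of trials, with responders' baseline about 0.21 to 0.27 mmol/L higher.
- An arm-by-baseline term on percentage change is significant in about 4 to 6%.
- The same term on absolute change, with the 5% effect, is significant in about 9 to 18%, because a uniform 5% is a larger absolute fall at higher LDL.

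**5. Other characteristics.** Simulated with 56 and 57 per arm, SD 8.57% and a 5% effect. The factor's correlation with LDL change is assumed and equal in both arms (no modification). The loss column takes the plan's 20% loss in the advice arm with baseline imputed, which lowers advice-arm responders from 28% to about 22%.

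| Correlation | 27f flags, no loss | 27f flags, 20% loss | Arm-by-factor term flags |
|---|---|---|---|
| 0 | about 5% | about 5% | about 5% |
| 0.1 | about 8% | about 7% | about 5% |
| 0.2 | about 20% | about 15% | about 5% |
| 0.3 | about 39% | about 30% | about 5 to 6% |

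For a real modifier (correlation 0.3 in the advice arm only), 27f detects about 39% without loss and 30% with it. The interaction detects about 36% and 25%. So at correlation 0.3, 27f flags a non-modifier about as often as a true modifier.

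**The case against.** 27f asks which characteristics are associated with success, largely through descriptive statistics; it does not claim to find who benefits because of the advice. For that literal question, a factor that correlates 0.3 with LDL change really is associated with success, and 39% is power rather than an error rate. This stands: a reader might infer that 27f's P-values are invalid, and the documents do not support that. What 27f cannot do is support the reading that its labels invite.

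A reader might also infer that the plan never looks at effect modification. It does so for age (<65 against 65+), to see whether results are homogeneous, though no test is named. Nor did the protocol promise modification tests: its phrase about factors likely to modify effects introduces adjustment covariates.

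That control-arm LDL plays no part in 27f is the likelier reading, not a certainty. Read literally, 27f could tabulate LDL responders in both arms, and secondary outcome no. 4 counts 10% LDL falls without restriction to one arm. Neither supplies a between-arm contrast for any listed characteristic.

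The 10% cut is deliberate: it is a stated aim and the threshold in the feedback letter. It deserves to stay as a descriptive outcome. Finally, SAP item 16 calls secondary outcomes mainly hypothesis generating, and interaction tests at this size are weak. Both points stand and limit the weight of this one.

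**Conclusion.** The point holds as an inexpensive improvement to an exploratory analysis. The within-arm contrast in 27f cannot distinguish predictors of response to the advice from predictors of ordinary LDL variation, and it builds regression to the mean into the baseline-LDL comparison. Under the planned effect, the rate of 10% falls expected without advice is about 33 to 43% of the advice-arm responder rate. The lower figure rests on the protocol's CV and the upper on a back-solved SD; both assume the same percentage effect in everyone. The flagging rates rest further on the assumed between-person SDs and correlations.

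Two stronger readings fail. Not every listed characteristic is distorted: one unrelated to LDL change keeps about 5% false positives. The primary between-group result at 6 months is not affected. Apart from the age subgroup, no modification analysis is planned for the factors that the protocol names: baseline LDL, BMI and sex have none.

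**What to change.** - For the true baseline characteristics (baseline LDL, BMI, age, sex, diabetes, impaired fasting glucose, blood pressure), model LDL change in both arms with an arm-by-characteristic term, one at a time. Use percentage change, already defined in SAP 26c, or the log ratio, so that the model matches the 10% responder scale. Absolute change, as in the planned GLM, would tend to flag baseline LDL even under a uniform percentage effect.
- Report each interaction estimate with its 95% CI, labelled exploratory.
- Use the same interaction term for the age <65 against 65+ subgroup.
- Keep the responder/non-responder tables as description, state which lipid defines response in each arm, and show LDL responders of both arms side by side.
- Report X:s and stated reasons separately as post-allocation variables. Both are recorded on the sheet in the allocation envelope, and the advice on that sheet differs by arm.

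The cost is SAP wording and a few model terms on data already collected. The downside is low power: about 25 to 36% for a strong modifier, slightly below the within-arm contrast. A non-significant interaction should therefore not be read as evidence of a uniform effect.

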- What are the reasons given for wanting to reduce LDL cholesterol? Is there any association between reasons given and effect on LDL cholesterol?

Section 3. Study Methods

9. Trial design

The study design is a pragmatic randomized controlled dietary trial, with two parallel arms. The allocation ratio is 1:1. Both groups will receive dietary advice in sealed numbered envelopes. The intervention group will receive advice for reducing LDL cholesterol, whereas the control group will receive similar advice, but instead proven effective for reducing fasting triglycerides. The participants will not be aware of which group is considered as active intervention. Participants were recruited and randomized May to October 2018 and data collection is finished April 18th 2019.

10. Randomization

The allocation sequence is created by an external agent and performed in blocks (size unknown to investigators). The allocation sequence will be concealed until data collection has been completed.

11. Sample size

A primary power calculation was performed based on previous randomized intervention studies of dietary fat quality and effects on lipoproteins. At least n=222 participants were required (for alpha = 0.05 and beta = 0.10) to detect an effect in LDL cholesterol of 0.175 mmol/L (~5%), which would slightly exceed that in most previous studies, parallel within-individual day-to-day variation (at double sampling), and have some clinical significance. This calculation took into account a 20% loss to follow-up in the intervention group and a contamination effect of 5% in the control group.

In September 2018, during the end of recruitment process, another power calculation was performed in order to examine the power given the current recruitment status (n=104). For alpha = 0.05 and beta = 0.20, the minimum number of participants required was n=106 (n=94 without 5% contamination). Thus, the recruitment was considered as finished at Oct 16th, when n=113 participants were included (as the number of volunteer participants had faded, and power was considered sufficient, if not optimal).

12. Framework

The study is a dietary intervention with clinical and experimental outcomes.

13. Stopping interim analyses

N/A.

14. Timing of final analysis

All analyses will be performed once data collection is finished, April 18th 2019.

15. Timing of outcomes assessment

N/A.

Section 4. Statistical principles

Confidence intervals and P values

16. Level of statistical significance

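### SAP 27f looks for baseline predictors of response only after cutting the measured change at 10%, which loses an estimated 42–47% of the LDL information in arms of about 56

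*SAP*

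**What the plan says.** SAP 27f (planned subgroup analyses) begins "In order to investigate whether different baseline characteristics are associated with success rate (outcome no. 4), responders". It then sets "responders (≥10% decrease in LDL cholesterol or Triglycerides) and non-responders at 3 weeks" side by side on age, sex, baseline cholesterol, diabetes, impaired fasting glucose, blood pressure, number of X:s in the food record and stated reasons, "separately for both study arms". It adds: "Comparisons between responders and non-responders will be analyzed by t-tests and Fisher's exact test". The same is planned at 6 months.

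SAP 26c applies to every continuous variable: "Relative change from baseline (% Δ) will be calculated as" the difference from baseline divided by baseline. The full-scale quantity therefore exists for each participant.

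Other sections use continuous change for some of the listed items. 27a plans linear regressions of LDL change (triglycerides in the control group) on the number of X:s. It also tabulates mean change by stated reason, and 26a lists associations of reasons with LDL change. After 27f, the SAP adds a subgroup analysis below v at or above 65 years. Baseline value, BMI, age and sex enter the general linear model in 27b, but only as adjustment covariates.

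**The concern.** Cutting a measured change at 10% treats a 9.9% fall like a rise, and a 10% fall like a 25% fall. For age, sex, diabetes, impaired fasting glucose, blood pressure and baseline cholesterol, the comparison across that cut is the only within-arm predictor analysis planned, apart from the two-way age split. In arms of about 56, with perhaps 13 to 17 responders, a moderate predictor could easily be reported as showing no difference between responders and non-responders, although the data to detect it are already collected.

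**Working it through.** **Inputs from the documents.** SAP section 11: recruitment closed "when n=113 participants were included"; effect 0.175 mmol/L, about 5%; totals of 222 (90% power, 20% loss, 5% contamination), 106 (80% power, 5% contamination) and 94 (80% power, no contamination). SAP section 9: "The allocation ratio is 1:1", so 113/2 is about 56 per arm. Protocol, Statistical analyses: a biological CV of 5% with double sampling. Alpha is 0.05, taken as two-sided.

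**Step 1: the plan's own figures.** No SD is stated. With n per arm = 2(z_α/2 + z_β)²SD²/δ², one value, SD = 0.30 mmol/L, gives all three totals:

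- 2 × (1.960 + 0.842)² × 0.30²/0.175² = 46.1, so 47 per arm, total 94.
- 47/0.95² = 52.1, so 53 per arm, total 106 (no allowance for loss to follow-up).
- 2 × (1.960 + 1.282)² × 0.30²/0.175² = 61.8, so 62; 62/(1 − 0.20 − 0.05)² = 110.2, so 111 per arm, total 222.

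Mean LDL is about 0.175/0.05 = 3.5 mmol/L. Solving back from exactly 47 per arm gives SD 0.303, and 0.303/3.5 = 8.65%. I take this as the SD of percentage change. The 5% CV gives a lower value, 5% × √2 = 7.1%; the upper value of 10% is assumed.

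**Step 2: information kept by the cut.** Assume a normal distribution and a mean fall of 5%. Then z = (−10 + 5)/SD, the responder share is p = Φ(z), and the information kept is φ(z)²/[p(1 − p)].

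| SD of % change | Responders | Kept | Lost | 56 people count as |
|---|---|---|---|---|
| 7.1% | 24% | 53% | 47% | 30 |
| 8.65% | 28% | 56% | 44% | 32 |
| 10% | 31% | 58% | 42% | 33 |

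**Step 3: power for a continuous characteristic.** Simulation with n = 56: linear regression on percentage change v a t-test of the characteristic across the cut.

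| True correlation | Full scale | After the cut (SD 7.1 / 8.65 / 10%) | Loss in points |
|---|---|---|---|
| 0.37 | 81% | 53 / 55 / 57% | 28 / 26 / 25 |
| 0.30 | 62% | 37 / 39 / 40% | 25 / 23 / 22 |
| 0.20 | 32% | 19 / 20 / 20% | 12 / 12 / 11 |

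Separate runs at a correlation of 0.364 with 24% responders lost 28.6 points. The range is therefore about 22–29 points where the full-scale test has 60–80% power, and 11–13 at a correlation of 0.20. At 0.10 the loss is only about 3 points.

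**Step 4: binary characteristic.** SD 8.65%, with a 6.7-point difference in percentage change, chosen so that the full-scale test has about 80% power in a 50:50 split. At 50% prevalence, the t-test on change has 81% and Fisher's exact test 47%, a loss of about 34 points. At 10% prevalence (6 of 56) it is 42–44% v 29–30%, about 14 points. The latter holds when the rarer group has the larger fall. With the difference reversed, Fisher's test has about 1% power against 42%, so the loss at low prevalence depends on direction.

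**Step 5: imputation.** SAP section 28 carries the baseline value forward. With 20% of the arm set to no change (correlation 0.364, SD 8.57%), power is 67% v 42%, so the loss is still about 25 points.

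No SD is given for triglycerides, so the same calculation cannot be made for them.

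**The case against.** The strongest reply is that 27f asks about the success rate, and success is defined by the 10% threshold. Which patients reach the target is a fair descriptive question, and a slope for mean change answers a different one. This stands. The threshold is also not merely a device of the feedback letter. It is in the Specific aims of both documents: the proportion reaching it, the effect in responders and the cost per person reaching it. The aim on misclassification rests on it too. So the responder comparison should stay. What does not follow is that it should be the only look at predictors: a characteristic that shifts the LDL response also shifts the chance of passing 10%, and the full scale shows that shift more precisely.

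Second, SAP section 16 calls the secondary outcomes mainly hypothesis generating, and 27f speaks of descriptive statistics. This stands too and limits the importance of the point, although 27f still plans tests.

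Third, a reader might infer that the plan never relates the listed items to continuous change. The documents do not support that: X:s and stated reasons have such analyses, and age has a subgroup analysis. The gap is limited to the baseline characteristics named above.

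Fourth, the size depends on the correlation assumed. For weak predictors neither method has useful power.

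**Conclusion.** The point holds as a cheap improvement to an exploratory analysis. For LDL, the cut loses about 42–47% of the information. For a continuous characteristic this costs about 22–29 points of power where the full-scale test would have 60–80%, and about 11–13 points at a correlation of 0.20. For a binary characteristic with a 6.7-point difference it costs about 34 points at 50% prevalence and about 14 at 10% if the rarer group responds better. These figures rest on a mean fall of 5%, an SD of 7–10% (24–31% responders), normality and a two-sided 5% test.

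Three stronger readings are tempting. One is that 27f is the plan's main analysis of who benefits. Nothing in the documents gives it that standing, and change within an arm is not benefit against control. Another is that every real predictor becomes a coin toss; that is true only near the correlations that give the full-scale test about 80% power. The third is a larger LDL loss in the control arm, where the mean change may be near zero. SAP 27a pairs the control group with triglycerides, so that case is not clearly planned. The primary result is unaffected.

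**What to change.** In SAP 27f, make linear regression of continuous percentage change the main predictor analysis for age, sex, diabetes, impaired fasting glucose and blood pressure. Use LDL in the intervention arm and triglycerides in the control arm, at 3 weeks and 6 months, and report each slope with its 95% confidence interval. If triglycerides are skewed, use the log of the ratio of follow-up to baseline, since a percentage change can be negative and cannot itself be logged.

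Baseline cholesterol needs separate wording. Baseline LDL is the denominator of its own percentage change, so the slope reflects mathematical coupling and regression to the mean. Either say so beside the estimate or leave it out of the regressions.

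Keep the responder/non-responder comparison as a descriptive profile for the 10% aim. The X:s and stated reasons need no new analysis.

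The cost is a few sentences in the SAP and some regressions in SPSS, with no new data. The downside is a few more exploratory estimates, which read as change per unit of the characteristic rather than as a responder profile.
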